The primary objective of the study is to investigate the adjunct effect of online tDCS with cognitive training on specific cognitive domains in stable schizophrenia patients. (i) right after the intervention (ii) whether maintenance effect at 1 month after intervention.

The secondary objective of the study is to probe (i) any effects on affective, psychotic and negative symptoms; (ii) psychosocial functioning, cognitive insight, subjective quality of life (QOL); (iii) the motivation and enjoyment of continuing playing the computerized cognitive training; (iv) the tolerability and adverse events of tDCS among patients with schizophrenia.

Hypotheses:

1. Concurrent cognitive training with online transcranial direct current stimulation(tDCS) will result in greater incremental training effect in specific cognitive domains as compared to cognitive training alone.

2. The cognitive effect in concurrent cognitive training with online tDCS will be maintained over time.
3. tDCS will have no effect on the affective, psychotic or negative symptoms, as compared to the control group(sham stimulation).

Methodology:

Study design

It will be a parallel-group, double-blinded, randomized controlled trial. It will be a 1-week intervention (5-week observation). Subjects will be randomized into two groups:

1. The intervention group- active stimulation of tDCS in ‘online’ mode +cognitive training
2. The control group- sham stimulation of tDCS + cognitive training

Subjects will be blinded to the allocation with group ratio of 1:1. The schedule, environment and equipment used for both groups will be identical. The study will observe the CONSORT guideline.

Study population and recruitment

Recruitment strategies include a convenience sample of patients with stable schizophrenia who will attend Psychiatric Day Hospitals in Tai Po Hospital. Informed consent will be obtained from each eligible subject.

Inclusion criteria: aged 18-65, right handed, understand and speak in Cantonese, diagnosis of schizophrenia meeting the diagnostic criteria of the World Health Organization’s 10th version of the International Statistical Classification of Disease and Related Health Problems (ICD-10). The screening of subjects will be made clinically by the study psychiatrist based on ICD-10.

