Exclusion criteria: 1) History of significant head trauma; 2) active abuse of alcohol or illegal substances; 3) significant neurologic history such as dementia, stroke, seizure, Parkinson’s disease, multiple sclerosis; 4) concurrent use of cognitive-enhancing medications e.g. acetylcholinesterase inhibitors ; 5) documented history of learning disability; 6) implanted with pacemakers, intracranial electrodes, defibrillators; 7) changes in medication regime over the 2 weeks before or during the study period.

Ethical consideration

The study will be performed in accordance with the Declaration of Helsinki (1964). All participants should take part in the study under voluntary basis. Written, informed consent will be obtained from all participants before inclusion in study, which will be submitted to the CUHK-NTEC Clinical Research Ethics Committee for approval. The study will be conducted in the Psychiatric Day Hospital in Tai Po Hospital. Any participant can withdraw from the study at any time point without the need of explanation. It will not affect the usual care of the participant.

Intervention

Within one week, subjects will receive 5 tDCS sessions applied concurrently with cognitive training on 5 consecutive days (a total of 5 sessions, each 20 minutes) . Participants will have 20 minutes of tDCS stimulation concurrently with 20 minutes of computerized cognitive training.

Based on the most recent metanalysis on tDCS in neuropsychological measures schizophrenia, when the number of tDCS session is not fewer than 5 sessions, no direct trend is identified between the amount of tDCS sessions and neuropsychological measures [24] .

Intervention apparatus:

tDCS Apparatus

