Both the assessor and the subjects will be blinded to the procedure. All subjects are assessed by the study psychiatrist who is blinded to the group allocation. Sham stimulation is generally regarded as an effective blinding technique, especially for those who have never experienced tDCS before[41]. All subjects will not be informed of the group allocation neither.

Definitions and Time Point of Measurements

At baseline(T0, at week-0), after the eligibility of the subjects are confirmed and consent to participate is obtained, the following will be assessed 1) clinical and demographic characteristics of the sample include 2) the primary outcome measure and 3) the secondary outcome measures. At completion of the intervention (T1, at week-1), and one month after the intervention (T2, at week-5), the primary and secondary outcome measures of the subjects will be measured.

i.Clinical and Demographic Characteristics

The subject characteristics include age, gender, handedness, years of education and employment status will be collected. Clinical data, including diagnosis, duration of illness, dosage of medications, daily exercise level and insight will be assessed.

ii. Primary Outcome Measure

Cambridge Neuropsychological Test Automated Battery (CANTAB) will be used as the primary outcome measure. [10] CANTAB is a computerized assessment that is automated and does not rely on the assessors' subjective assessment. It has standardized automated test delivery with systematic scoring and automated saving. Practice effects are eliminated with parallel mode and stimuli randomization. It has concurrent validity same as the MATRICS consensus cognitive battery (MCCB). Due to the sensitivity of CANTAB, it can detect effects in small effect size over shorter period of time. Test-retest reliability is > 0.7 , which is consensed opinion for cognitive evaluation in schizophrenia. Computerized CANTAB tasks on specific cognitive domains on paired associates learning, working memory, processing speeds and executive function will be selected.

iii. Secondary Outcomes Measures

Measures on Affective , Psychotic and Negative Symptoms

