- Positive and Negative Syndrome Scale (PANSS) [42] is a 30-item clinician rated questionnaire to assess the symptoms in schizophrenia patient. It has 3 sub-categories of positive symptoms, negative symptoms and general psychopathology. It is shown to have good construct validity , internal reliability and inter rater reliability. [43] It is also shown to be sensitive to change. [44] The assessment time is around 40-50 minutes.
- Calgary Depression Scale for Schizophrenia [45, 46] is a 9-item clinician rated and is administered following a semi-structured interview. It has been used by other tDCS studies in schizophrenia, and it has been shown to be reliable , valid and sensitive to depressive symptoms separate from positive, negative and extrapyramidal symptoms in schizophrenia. A score above 6 has 82% specificity and 85% sensitivity for predicting the presence of a major depressive episode.

- Clinical Global Impression Scale (CGI) [47]- Schizophrenia is a 3-item clinician rated questionnaire to assess illness severity, global improvement or change, and treatment response.

Measures on Psychosocial Functioning

- Social and Occupational Functioning Assessment scale (SOFAS)[48]
- World Health Organization Five Well-Being Index (WHO-5) is a 5-item self reported questionnaire of subjective quality of life (QOL). [49, 50]

Ratings on Motivation and Enjoyment on Cognitive Training

- Visual Analog Scale to rate their motivation and enjoyment to continue playing the computerized cognitive training game (scores ranged from 0-100, with higher scores indicating enhanced enjoyment/ willingness to come)

Tolerability on tDCS

- An Adverse Effects Questionnaire associated with t-DCS administration, which is generated from a systematic review in 2011 by Brunoni. [51]

Clinical Insight

- Beck Cognitive Insight Scale Taiwanese Version is 15-item self reported questionnaire with two subscales (nine items tapping self-reflectiveness and six on self-certainty); it is shown to have Cronbach's alpha values of >0.70 for both subscales and moderate stability.[52, 53]

Statistical Analyses:

The data will be collected according to the Intention-to-treat(ITT) protocol, with last observation carried forward (LOCF) design i.e. all subjects whose baseline data collected and performed at least 1 day of stimulation will be included in the analysis. The missing observation due to non-compliance will be imputed accordingly to the last assessment performed.

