The baseline demographics and baseline clinical characteristics (T0) will be compared between the group of active tDCS and sham tDCS with Pearson's chi-square test (for categorical variables) and independent-sample t tests (for continuous variables).

Linear mixed effect models will be used for each outcome measures, using the covariates of group (tDCS versus sham) and time (T0, T1 and T2).

Pearson's correlation test will be performed to evaluate whether there will be correlation between change in cognitive performance vs demographics and baseline clinical characteristics.

Statistical significance will be referred to a two tailed p-value of less than 0.05.
All computations will be performed using SPSS for Mac OS and Microsoft for excel.

Data Management:

Raw data and electronic data will be stored in locked space and password protected computers respectively. All data will be destroyed 5 years after completion of study and submission for publication.

Sample size estimation :

The effect in difference found in the specific cognitive domains between the tDCS and sham group before and after the intervention in the similar studies was 0.31 (Smith et al., 2015), 0.21 (Lam, 2016), 0.6 (Nienow et al., 2016) represented by partial eta square. Considering the medium to large effect size of the studies, it is difficult to replicate a study with a large effect size. Hence, the rule-of-thumb medium effect size Cohen's F 0.25 was chosen as the partial eta square. Considering a power of 80% and a critical alpha of 5%, it was estimated that a total of 44 patients would be needed in total. .

Safety Consideration:

Concerning the safety profile, tDCS is generally regarded as safe for short-term administration. There is no published report that tDCS has to be discontinued for safety reasons. The adverse effects of tDCS have been reported to be minimal and its risk of inducing seizure is minimal. Meta-analysis suggested that tDCS is associated with mild adverse effects only, such as itching, tingling, mild burning or pain sensations. [51]In particular, mild burning is related to administration of electric current with higher contact impedance. In our study, we will use the StarStim 8 (NeuroElectrics, Barcelona, Spain). StarStim 8 will not operate if the contact impedance is above 20 kOhm, which is the far from the threshold for tissue damage.

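### Last observation carried forward builds the one-month maintenance under test into the data of patients lost after T1; the planned mixed model does not need the imputation

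*Combined protocol and SAP*

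**What the plan says.** The Statistical Analyses section of the combined protocol and SAP announces an intention-to-treat analysis with last observation carried forward (LOCF). The analysis set is generous: "all subjects whose baseline data collected and performed at least 1 day of stimulation will be included in the analysis". Gaps are filled by this rule: "The missing observation due to non-compliance will be imputed accordingly to the last assessment performed". The same section plans a linear mixed model for each outcome, "using the covariates of group (tDCS versus sham) and time (T0, T1 and T2").

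Assessments take place only at baseline (T0), at the end of the treatment week (T1) and at week 5 (T2). The second part of the primary objective asks "whether maintenance effect at 1 month after intervention", and Hypothesis 2 reads: "The cognitive effect in concurrent cognitive training with online tDCS will be maintained over time".

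The plan gives no reason for LOCF, no expected dropout, no missing-data assumption and no sensitivity analysis.

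**The concern.** With three assessments, LOCF can do only two things.

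- **Seen at T1, missed at T2.** The T1 score is copied to T2. For that patient the data now say that whatever was present after treatment is still there a month later. This is the answer to the maintenance question, supplied by the imputation.
- **Lost before T1.** The baseline score is copied to both later visits, so the patient is recorded as having gained nothing. The analysis set admits such patients after a single day of stimulation.

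Neither step is needed to keep partly observed patients in the analysis, because a likelihood-based mixed model accepts incomplete records. At stake is the T2 result: if the effect fades and patients are lost after T1, a claim of benefit at one month becomes more likely than the nominal error rate allows.

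**Working it through.** **Inputs from the plan.** Visits T0, T1 and T2; 44 patients allocated 1:1, so 22 per arm; two-sided 5% level. The plan states no figure for missing data, so there is none to reproduce.

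**Assumed inputs.** Loss of 10, 20 or 30%, equal between arms and unrelated to outcome. All gaps filled. SD 1 at each visit and correlation 0.7 between visits (the plan says only that test-retest reliability exceeds 0.7). A true effect of 0.5 SD at T1: the sample size section takes a medium Cohen's f of 0.25, and for two equal groups d = 2f = 0.5, but that section names no test.

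**Step 1. Loss after T1 only.** Let d1 and d2 be the true group differences at T1 and T2, and q the share lost between them. The expected T2 contrast under LOCF is

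(1 − q)·d2 + q·d1, so the bias is q·(d1 − d2).

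The bias is positive if the effect fades, zero if it persists and negative if it grows.

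| True d2 (d1 = 0.5) | q = 10% | q = 20% | q = 30% |
|---|---|---|---|
| 0 (gone) | 0.05 | 0.10 | 0.15 |
| 0.25 (half left) | 0.275 | 0.30 | 0.325 |
| 0.5 (persists) | 0.50 | 0.50 | 0.50 |

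**Step 2. Error rate when the effect is gone at T2.** The standard error of the change-score contrast is √[2(1 − 0.7)·2/22] = 0.234 SD. Simulation with 40,000 runs per cell, t-test on T2 − T0:

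| Loss after T1 | Two-sided rejection | Rejection favouring active |
|---|---|---|
| 0% | about 5% | about 2.5% |
| 10% | about 5.4% | about 4% |
| 20% | about 7% | about 6% |
| 30% | about 9.3% | about 9% |

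The last column is the one that bears on a false claim of lasting benefit. An unstructured mixed model on the observed data gave two-sided rates of 4.8/5.2/5.2% at 10/20/30% loss (20,000 runs per cell).

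**Step 3. Loss before T1.** Let p be the share lost in each arm. The T1 contrast under LOCF is (1 − p)·d1: 0.9 × 0.5 = 0.45 at 10% and 0.8 × 0.5 = 0.40 at 20%. Whether this is bias depends on what these patients' scores would have been.

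- If they would have gained as the rest of their arm did, the truth is 0.50, and LOCF understates it by 0.05 or 0.10.
- If they truly gained nothing, the contrast over all patients is (1 − p)·0.5 + p·0 = 0.45 or 0.40. LOCF is then right on average, and a mixed model assuming missing at random, which targets 0.50, overstates it.

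**Step 4. Both kinds of loss.** If early dropouts would have gained like the others, the T2 contrast is (1 − p − q)·d2 + q·d1. With 20% total loss, d1 = 0.5 and d2 = 0.25:

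- p = 5%, q = 15%: 0.80 × 0.25 + 0.15 × 0.5 = 0.275
- p = 10%, q = 10%: 0.80 × 0.25 + 0.10 × 0.5 = 0.25
- p = 15%, q = 5%: 0.80 × 0.25 + 0.05 × 0.5 = 0.225

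The net direction depends on the mix, so LOCF cannot be called reliably conservative.

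**The case against.** The strongest reply is that the practical effect may be slight. Treatment lasts five consecutive days and follow-up ends at week 5, so loss may be low. The headline case needs the effect to vanish completely. With half of it left, the bias is 0.025 to 0.075 SD against a standard error near 0.23. With full persistence it is zero. At 10% loss, rejection favouring active rises by only about 1.5 percentage points. The rule also names only gaps due to non-compliance. If half the gaps were filled and the rest left missing, the spurious effect would be 0.5·(q/2)/(1 − q/2), or 0.026/0.056/0.088 SD. All of this stands and limits the size.

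A second reply concerns early loss. A reader might infer that LOCF necessarily understates a real effect when patients leave before T1. The documents do not support that. Under the stated intention-to-treat principle, what matters is how a patient actually fares after stopping, and someone who had one or two of five sessions may have gained little. The plan does not settle this, so the early-loss effect is conditional.

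Neither reply answers the T2 problem: copying T1 to T2 assumes the result that the visit is there to measure.

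**Conclusion.** The concern holds in a limited form and should be fixed. LOCF conflicts with the maintenance question by construction, whatever the dropout rate, and the planned model makes it unnecessary. Under equal loss after T1 it overstates a fading effect, leaves a persisting one unbiased and understates a growing one. For loss before T1 it imposes a no-gain assumption that may or may not be close to the truth.

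The size is unknown, because no dropout rate is given. The illustration (spurious T2 effect of 0.05/0.10/0.15 SD, rejection favouring active of about 4/6/9% against about 2.5%) rests on complete fading from 0.5 SD, correlation 0.7, every gap filled, and equal loss unrelated to outcome. A reader might go further and infer that the trial's one-month result will be materially wrong; the documents do not show that.

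Which gaps would be filled is also open. Non-compliance is not defined, and the ethics section says: "Any participant can withdraw from the study at any time point without the need of explanation". This adds uncertainty about how the rule would be applied, but it is not the core of the point.

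**What to change.** Replace LOCF as the main approach. Fit the planned mixed model by REML to all observed T0, T1 and T2 data, with a group-by-time term that gives the treatment contrasts at T1 and T2 (the current text names only group and time). Keep LOCF at most as a sensitivity analysis. Add one simple sensitivity analysis for data not missing at random, including a no-gain assumption for patients who stopped before T1.

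The cost is a change of SAP wording and a little extra analysis, with no new visits or patients. The main analysis would then rely on missing at random, which is why the sensitivity analysis belongs with it. Standard errors for the T2 contrast widen slightly: 0.24 against 0.23 SD at 10% missing and 0.26 against 0.24 SD at 30%, comparing an unstructured model on observed data with a change-score test on filled data.

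### Baseline significance tests between randomised arms tell the reader little at about 22 per arm, while the outcome model leaves out prognostic variables already collected; the cost is mainly precision, not overall type I error.

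*Combined protocol and SAP*

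**What the plan says.** Under Statistical Analyses, "The baseline demographics and baseline clinical characteristics (T0) will be compared between the group of active tDCS and sham tDCS". The tests named are chi-square for categorical characteristics and the two-sample t test for continuous ones. The significance rule is general: "Statistical significance will be referred to a two tailed p-value of less than 0.05". No consequence is attached to a significant or a non-significant baseline result.

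The same section plans linear mixed models for each outcome, "using the covariates of group (tDCS versus sham) and time (T0, T1 and T2"). No group-by-time term and no prognostic covariate is named. T0 is one of the modelled time points.

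Under Clinical and Demographic Characteristics, "The subject characteristics include age, gender, handedness, years of education and employment status will be collected", together with diagnosis, illness duration, medication dosage, exercise level and insight. Apart from the baseline comparison, their only stated use is an exploratory Pearson correlation with cognitive change.

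The Randomization procedure is 1:1 in blocks with no stratification factor stated. On size, "it was estimated that a total of 44 patients would be needed in total".

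**The concern.** When allocation is random, any baseline difference between arms arose by chance. A test of that null cannot reveal anything about the allocation: a significant result is a false alarm, and a non-significant one does not show that the arms are alike. In a small trial a sizeable difference can go unflagged.

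The eligible age range is 18 to 65, and age and education plausibly predict cognitive test scores. If they do, leaving them out of the model discards precision that the trial has already paid for. It also leaves the estimate exposed to whatever imbalance occurs in the one randomisation actually carried out. At stake are the width of the interval for the active-sham difference on CANTAB and how far a reader can rely on the baseline table.

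**Working it through.** **Inputs from the documents.** N = 44 at 1:1, so 22 per arm; two-sided alpha 0.05; Cohen's f = 0.25, which for two groups is d = 2f = 0.5. Ten baseline characteristics are listed. Handedness and diagnosis are fixed by the inclusion criteria, so about eight can vary.

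**Assumptions (not in the documents).** Correlation rho between T0 and a later score: 0.5 to 0.8. The only related figure is the test-retest reliability above 0.7. Correlation r of a covariate with the score: 0.3 to 0.6, unless stated otherwise.

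**1. What the baseline t test can flag.** SE of a standardised difference = sqrt(2/22) = 0.302. Critical value = t(0.975, 42 df) × SE = 2.018 × 0.302 = 0.61 SD. An observed 0.3 SD gives p = 0.33 and 0.5 SD gives p = 0.105. For a binary characteristic, 8/22 against 14/22 gives chi-square p = 0.07.

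**2. Chance of an unflagged imbalance, per variable.** P(|difference| > x) − 0.05:
- x = 0.3 SD: 0.325 − 0.05 = 0.28
- x = 0.4 SD: 0.192 − 0.05 = 0.14
- x = 0.5 SD: 0.105 − 0.05 = 0.05

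**3. False flags.** 1 − 0.95^8 = 0.34 for eight tests, if independent.

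**4. Shift caused by an imbalance of 0.5 SD.**
- Covariate, score levels compared: r × 0.5 = 0.25 SD at r = 0.5 (0.15 to 0.30 for r = 0.3 to 0.6), against d = 0.5.
- Covariate, change from T0 compared: (r with later score − r with T0) × 0.5. This is zero if the relation is the same at both times. If the two differ by 0.1, it is 0.05 SD.
- The T0 score itself, change compared: (1 − rho) × 0.5 = 0.25, 0.15 or 0.10 SD at rho = 0.5, 0.7 or 0.8, in the opposite direction to the imbalance. Adjusting for the T0 score removes it.

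**5. Type I error.** Simulation of 40,000 null trials, 22 per arm, one post-baseline time point. The last two columns cover only trials with an unflagged T0-score imbalance of about 0.40 to 0.61 SD.

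| Analysis | All trials | rho 0.5 | rho 0.7 |
|---|---|---|---|
| Change (group by time) | 5.1% | 8.9% | 7.5% |
| Group main effect over T0 and T1 | 4.9–5.1% | 12.6% | 11.9% |
| Adjusted for T0 score | 5.1–5.3% | 5.3% | 5.3% |

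**6. Precision.** Take rho = 0.7 and two independent covariates, each correlated r = 0.3 to 0.45 with both scores.
- Levels: residual variance 1 − 2r². At r = 0.4 this is 0.68, so SE = 0.302 × sqrt(0.68) = 0.25 (0.27 at r = 0.3, 0.23 at r = 0.45).
- Change: variance 2(1 − rho) = 0.60 with or without these covariates. Normal-approximation power for d = 0.5 is 57%.
- Adjusted for T0: variance 1 − rho² = 0.51, power 64%.
- Adjusted for T0, age and education: (1 − 2r²) − (0.7 − 2r²)²/(1 − 2r²) = 0.490, 0.468 and 0.449 at r = 0.3, 0.4 and 0.45. Power is 66%, 68% and 70%. A simulation with assumed correlations in the same range gave 61% rising to 63–73%.

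**The case against.** The strongest reply is that the trial's question concerns change. Hypothesis 1 speaks of an incremental training effect, the sample-size effect is a before-after difference, and T0 is in the model. Age and education hardly move in five weeks, so a constant effect of theirs cancels. That stands: the 0.25 SD covariate shift belongs to a comparison of levels and cannot be carried over to a change contrast. It does not dispose of the point, because the plan does not write a group-by-time term, and an imbalance in the T0 score does not fully cancel from change.

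Four stronger readings are tempting, and the documents do not support them.
- A reader might infer that the trial's error rate is inflated. Over all randomisations it is not (step 5).
- A reader might infer that trivial differences will be flagged. Nothing below about 0.61 SD can reach p<0.05 on the t test. A flag may fall on a variable of no prognostic importance, which is a different matter.
- A reader might infer that non-significance will be taken as balance, or that covariates will be picked from the p-values. The plan says only that the arms will be compared. It neither states nor rules out such use.
- A reader might infer a breach of the statement that "The study will observe the CONSORT guideline". The documents do not say what that guideline requires on baseline tests, so nothing here rests on it.

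The figures also need careful pairing. The 28% relates to unflagged imbalances of 0.3 SD or more; for 0.5 SD or more it is about 5% per variable. The 34% assumes independent tests, whereas age, illness duration, education and employment are probably related.

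**Conclusion.** The point holds in a limited form. The baseline tests are uninformative by design, and the outcome model uses none of the prognostic variables collected. The consequence is lost precision, plus distortion conditional on an imbalance having occurred.

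Most of the gain in a change setting comes from adjusting for the T0 score (power about 57% to 64% at d = 0.5, rho = 0.7). Age and education then add a modest amount (to about 66–70%). They add almost nothing to a pure change contrast, but they narrow a comparison of levels clearly (SE 0.30 to about 0.25). All of these rest on assumed correlations. No passage shows that age or education predicts CANTAB scores in this population, or change in them. The finding does not depend on whether 44 is the right sample size; it uses only 22 per arm. It is a worthwhile improvement to the SAP, not a threat to the trial's validity.

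**What to change.** 1. Drop the baseline p-values. Report means and SDs or counts by arm, with standardised differences.
2. Pre-specify, whatever the observed balance, that each CANTAB comparison at T1 and T2 adjusts for the T0 score of that measure, age and years of education. The T0 score may enter as a covariate, or the mixed model may hold a common baseline mean for both arms.
3. If T0 stays in the model as a response, add age-by-time and education-by-time terms, since main effects alone cancel from change.
4. State that covariates will not be chosen from baseline comparisons.

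The cost is SAP wording and some degrees of freedom: two for age and education, or 2 + 2 × 2 = 6 with interactions over three time points. A T0-score covariate, if used, takes one more. No new data, visits or patients are needed. The downside is little return if age and education do not predict the score beyond T0; the T0 adjustment then carries nearly all the benefit. The wording should be fixed before unblinding.

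### The mixed model names only group and time (T0, T1, T2); no term or visit contrast is stated as the test of hypothesis 1 or hypothesis 2

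*Combined protocol and SAP*

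**What the plan says.** The efficacy analysis is one sentence in the Statistical Analyses section. It gives a linear mixed model for each outcome, "using the covariates of group (tDCS versus sham) and time (T0, T1 and T2"). T0 is listed as a level of time, so baseline enters as an outcome visit and not as an adjusting variable. No interaction, baseline covariate, visit contrast or covariance structure is named here or elsewhere.

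Other sections point to an analysis of change:

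- Objectives: the effect is of interest at two times, "i) right after the intervention (ii) whether maintenance effect at 1 month after intervention".
- Hypothesis 1: active stimulation "will result in greater incremental training effect in specific cognitive domains as compared to cognitive training alone".
- Hypothesis 2: "The cognitive effect in concurrent cognitive training with online tDCS will be maintained over time".
- Sample size estimation: the effects taken from earlier studies are differences "between the tDCS and sham group before and after the intervention".
- Statistical Analyses, correlation paragraph: "change in cognitive performance vs demographics and baseline clinical characteristics".

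None of these is tied to a term of the mixed model.

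**The concern.** Hypothesis 1 is about a between-arm difference in change. A model whose only terms are group and time has one group coefficient, a constant active-sham difference assumed to be the same at T0, T1 and T2. Randomisation makes the expected T0 difference zero, so including that visit dilutes any effect. The same coefficient cannot separate the result straight after treatment from the result a month later, which is the distinction the objective draws.

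Even if an interaction was intended, several tests remain open: the two-degree-of-freedom interaction, the T0-to-T1 contrast, the T0-to-T2 contrast, or a baseline-adjusted comparison. They can give different p-values on the same data. Maintenance could mean T2 against T0 or T2 against T1. With nothing fixed in advance, the choice can follow the results.

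**Working it through.** **Does the planned sample size reveal the tested term?** Inputs from Sample size estimation: Cohen's f = 0.25, 80% power, 5% alpha, 44 in total. Not stated: the tested term, the number of visits m, and the between-visit correlation r. The usual noncentral-F formulas for two groups are:

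- Group-by-time: λ = f²Nm/(1 − r), with (m − 1) and (N − 2)(m − 1) df.
- Group main effect: λ = f²Nm/(1 + (m − 1)r), with 1 and N − 2 df.

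A total of 44 gives 80% power for the group main effect with m = 3 and r = 0 (80.1%). It also does so for group-by-time with r about 0.33 (m = 2) or about 0.17 (m = 3). The figure therefore does not identify the term. The term matters: with N = 44, m = 3 and r = 0.5, λ is 0.0625 × 132/0.5 = 16.5 for the interaction (power 96%) and 0.0625 × 132/2 = 4.125 for the main effect (power 51%). In these formulas f = 0.25 does not stand for the same SD difference in both tests, so these powers are not comparable with those below.

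**What the group term estimates if the sentence is followed literally.** Assume balanced complete data, compound symmetry and SD 1. The estimate is the mean of the three visit differences:

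- Sustained effect d: (0 + d + d)/3 = 2d/3, or 0.33 SD for d = 0.5.
- Effect halved by T2: (0 + 0.5 + 0.25)/3 = 0.25 SD.
- Effect gone by T2: (0 + 0.5 + 0)/3 = 0.17 SD.

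With no true effect the estimate is centred on zero. A simulation at r = 0.7 gave 4.8% rejections, so type I error is not inflated.

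**Power.** Assume 22 per arm, two-sided 5%, and noncentral t with 42 df. The correlation r between visits is an assumption. The Primary Outcome Measure section says "Test-retest reliability is > 0.7", but that is a general statement about the battery, so a range is shown. Standard errors:

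- Group term: √[(2/22)(1 + 2r)/3]
- T0-to-T1 change: √[(2/22) × 2(1 − r)]
- Baseline-adjusted T1: √[(2/22)(1 − r²)]. For power, the variance is multiplied by 1 + F(1,42)/42 (mean 1.025) for estimating the baseline slope, with 41 df.

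For example, at r = 0.7 the first two are √(0.0909 × 0.8) = 0.270 and √(0.0909 × 0.6) = 0.234. The ratios to SE are 0.333/0.270 = 1.24 and 0.5/0.234 = 2.14.

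Power for 0.5 SD sustained at T1 and T2:

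| r | Group term | T0-to-T1 change | Baseline-adjusted T1 |
|---|---|---|---|
| 0.1 | 40% | 23% | 36% |
| 0.3 | 32% | 28% | 39% |
| 0.5 | 26% | 37% | 46% |
| 0.7 | 23% | 55% | 61% |
| 0.8 | 21% | 73% | 76% |

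Simulation (40,000 trials) at r = 0.3 to 0.8 agreed to within 0.6 percentage points.

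If the effect halves by T2, the group term has 17% power at r = 0.5 and 15% at r = 0.7. If it is gone by T2, 10% and 9%.

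**Where the order reverses.** The group term and the change contrast have equal power when (4/9) × 2(1 − r) = (1 + 2r)/3, which gives r = 5/14 = 0.36. Against the baseline-adjusted contrast the condition is (4/9)(1 − r²) = (1 + 2r)/3, i.e. 4r² + 6r − 1 = 0, so r = 0.15 (0.16 with the slope estimated). Below those values the group term is the more powerful test, although it still cannot separate T1 from T2.

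**The case against.** The strongest reply is that the sentence lists factors and does not exclude an interaction. The hypotheses, the objective, the sample-size text and the correlation analysis all point to change, so a group-by-time model was probably meant. This stands as far as it goes: the text shows an incomplete specification, not a decision to fit the wrong model, and the power table is conditional on the literal reading.

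A second reply is that if the two-degree-of-freedom interaction is what gets tested, little power is lost for a sustained effect. Under the same assumptions (0.5 SD, 84 error df) its power is 37% at r = 0.5 and 58% at r = 0.7, against 37% and 55% for the T0-to-T1 contrast. That is also correct. But if the effect halves by T2, the interaction has 29% and 45%, and a significant interaction does not say which visit produced it.

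Third, the Objectives section and the visit definitions do fix T1 and T2 as the visits of interest. For hypothesis 1, what is open is therefore the term and the handling of baseline, not the visit. For hypothesis 2 the reference point itself is open, and its wording could even be read as a claim within the active arm only.

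These points narrow the size of the harm. None supplies the missing test.

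**Conclusion.** The concern holds and should be fixed. The plan does not state which estimate tests hypothesis 1 or hypothesis 2, or what counts as maintenance. That much depends on no assumption.

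The numerical loss is conditional. It applies if the additive model is fitted and its group term is used as the test. It then shrinks a sustained effect to two-thirds and a T1-only effect to one-third. At r = 0.7 and 0.5 SD sustained, power is 23%, against 55% for the T0-to-T1 contrast. The 0.5 SD effect, the correlation, compound symmetry and complete data are assumptions; the plan gives no correlation and intends last observation carried forward. At low correlation the power comparison reverses, but the inability to separate the two hypotheses remains.

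**What to change.** State the model as categorical time with a group-by-time term and within-patient correlated errors. Name the active-sham contrast in T0-to-T1 change as the test of hypothesis 1. For hypothesis 2, name the active-sham contrast in T0-to-T2 change, with its 95% confidence interval. If maintenance is meant as T2 against T1, or within the active arm, say so and report that contrast with its interval; a non-significant T1-to-T2 difference does not by itself show maintenance. The sample-size paragraph should then refer to the same contrast.

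Preferable, but not needed to meet the point: constrain the T0 means to be equal across arms, or use T0 as a covariate with T1 and T2 as outcomes. The variance relative to change from T0 is (1 − r²)/[2(1 − r)] = (1 + r)/2. That is 15% lower at r = 0.7 and 25% lower at r = 0.5, or about 13% and 23% after multiplying by 1.025 for the estimated slope.

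The cost is two sentences for the model and contrasts, plus a matching reference in the sample-size text. The data, visits and software are unchanged.
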